6.1.9. Visit 9 (Week 10-11 [+/- 2 weeks])+

Subjects will return to the Research Imaging Institute to undergo post-treatment Magnetic Resonance Spectroscopy/Imaging for intrahepatic liver fat measurement. Control group subjects will receive nutritional counseling, which may be performed by home visit or a video telehealth visit.

6.1.10. Visit 10 (Week 11-12) -- "Optional"

Participants will come to the research unit for vital signs and VO₂max testing (same as Visit 4) Control group subjects will receive nutritional counseling, which may be performed by home visit or a video telehealth visit.

6.1.11. Visit 11 (Week 11-12)

Subjects will arrive fasting to undergo vastus lateralis muscle biopsy, subcutaneous fat biopsy, and collection of blood and urine samples for research purposes. These samples will be used to evaluate treatment effects on tissue cellular senescence, oxidative stress, DNA methylation and mitochondrial function. Post-intervention blood laboratory assays also will be done for CMP, CBC, HbA1c, and lipid panel. Control group subjects will receive nutritional counseling, which may be performed by home visit or a video telehealth visit.

6.1.12. Visit 12 (Week 13)

Subjects will come to the research unit for evaluation of the biopsy sites. This visit may be conducted by home visit, telephone visit or a video telehealth visit. Control group subjects will receive nutritional counseling, which may be performed by home visit or a video telehealth visit.

6.2. Visit Schedule Summary

	VISIT 1	VISIT 2**	VISIT 3**	VISIT 4	VISIT 5	VISIT 6	VISIT 7	VISIT 8***	VISIT 9***	VISIT 10	VISIT 11	VISIT 12
Schedule	-17 days to -21	-7 days to -17, +/- 2wks	-7 days to -17, +/- 2wks	-1 days to -6	Day 0	Week 4	Week 8	Week 10-11, +/- 2wks	Week 10-11, +/- 2wks	Week 11-12	Week 11-12	Week 13
Consent	X											
Vital Signs	Х			Х						Х		
Medical History	Х											
Physical Exam	Х											
MoCA	Х											
Safety Labs (fastin	l ng):											
CBC	Х										Х	
CMP	Х					Х					Х	
Lipid Panel	Х										Х	
PT/PTT/INR	Х											
HbA1c	Х		_	_							Х	
Insulin	Х								_		Х	
FFA	Х										Х	
TSH	Χ											

⁺ Visits 8 and 9 may be performed interchangeably based on DXA and MRI scanner availability.

HSC 20190766H

Version: 2.4 10-29-2020

Routine UA	Х											
DXA		X						Х				
Liver Fibroscan		Х						Х				
MRS/MRI - RII			Х						Х			
Physical Performan	nce:											
Walk Distance		Х						Х				
Grip Strength		Х						Х				
Isom. Knee Ext		Х						Х				
VO2max CPET*				Х						Х		
Muscle Biospy					Х						Х	
SQ Fat Biopsy					Х						Х	
Research Labs:												
Blood					Х						Х	
Urine					Х						Х	
Nutrition consult an	d weight (c	ontrols)			Х	Х	Х					
Nutrition Phone Fol	low Up				weekly	weekly	weekly					
Treatment dispensed				Х	Х	Х						
Treatment Phone F	ollow Up				V5+1w	V6+2w	V7+2w					
Biopsy check						Х						Х
Assess AE		Х	Х	Х	Х	Х	Х	Х	Х	Х	Х	Х

^{*}CPET is optional (Visits 4 & 10)

6.3. Analyses.

Muscle (frozen): Protein oxidative damage will be evaluated from muscle biopsy tissue using immunoblotting against carbonylated protein side chains. DNA from muscle samples will be extracted and tested for 8-hydroxydeoxyguanosine (8-OHdG) content to evaluate oxidative DNA damage and total DNA methylation will be evaluated.

Muscle (fresh): Tissue obtained will be evaluated by an Oroboros Oxygraph-2k high-resolution respirometer to measure mitochondrial respiration capacity. Skeletal muscle fibers will be mechanically separated and permeabilized in BIOPS as described previously to allow uptake of mitochondrial electron transport chain substrates (25). Tissue will then be tested in MiRO6 buffer using a substrate-uncoupler-inhibitor titration (SUIT) protocol to evaluate oxidative phosphorylation capacity.

Fat (frozen): will be subjected to reverse-transcriptase qPCR for measurement of gene expression levels of senescence and SASP markers, including IL-6, TNFα, p16, p21, and MCP1.

Fat (fresh): tissue will be subjected to beta galactosidase staining to test cellular senescence in the tissue as described previously (42).

Blood/plasma: Circulating factors that include inflammatory markers IL-6 and IL-6R, AGE-RAGE levels, and SASP biomarkers such as plasminogen activator inhibitor (PAI) -1 and 2, intracellular adhesion molecule (ICAM)-1 and 2 will be tested using ELISA kits on blood samples obtained during study. 20mL of blood will be drawn (two (2) 10mL EDTA lavender top tubes), centrifuged to obtain 10mL of plasma, and stored in 0.5-1 ml aliquots to evaluate whether the treatment reduces pro-inflammatory blood markers of aging. Blood samples obtained during the glucose tolerance tests will be analyzed for insulin and free fatty acid concentrations. DNA methylation assays will be done in peripheral blood cells.

Urine: A fasted urine sample will be obtained at baseline and post treatment for urinalysis, microalbumin, excreted IL-6, and AGE-RAGE levels to evaluate changes with treatment. 2-5 ml aliquots will be stored frozen for analysis.

^{**}Visits 2 and 3 may be performed interchangeably

^{***}Visits 8 and 9 may be performed interchangeably

7. Statistical Plan

7.1. Sample Size Determination

The effect of SGLT2 inhibitors on aging-related biomarkers in pre-diabetic subjects is not known. The data generated through this study will guide sample size and power calculations for future studies.

7.2. Statistical Methods

Analytical Approach.

Experimental results will be expressed as means ± SE. Comparisons of means between all the groups will be done by ANCOVA. Associations, within a group, between aging-related biomarkers vs metabolic outcomes and vs. healthspan outcomes will be determined by Pearson's correlation. For tests of correlation coefficients between groups, we will use the Fisher's Z transformation. We will also determine the relationship between aging-related biomarkers vs metabolic outcomes and vs. healthspan outcomes, by using multiple regression analysis. Scatter plots will be done to look for outliers and to verify linearity.

We will use natural logarithmic transformation to evaluate median percent change. This pilot study is not powered to achieve statistical significance with a p <0.05 and is of exploratory nature. The data included in this study will be only of completers. A larger trial in the future based on this pilot data would follow an intention-to-treat analysis.

The Biostatistics Core of the San Antonio Pepper Center, led by [name], will guide the statistical analyses.

8. Safety and Adverse Events

8.1. **Definitions**

Unanticipated Problems Involving Risk to Subjects or Others (UPIRSO)

Any incident, experience, or outcome that meets all of the following criteria:

- Unexpected in nature, severity, or frequency (i.e. not described in study-related documents such as the IRB-approved protocol or consent form, the investigators brochure, etc.)
- Related or possibly related to participation in the research (i.e. possibly related means there is a reasonable possibility that the incident experience, or outcome may have been caused by the procedures involved in the research)
- Suggests that the research places subjects or others at greater risk of harm (including physical, psychological, economic, or social harm).

Adverse Event (AE)

In general, AE is used very broadly and encompasses physical and psychological harms and includes:

Any untoward or unfavorable medical occurrence in a human subject, including any abnormal sign (for example, abnormal physical exam or laboratory finding), symptom, or disease, temporally associated with the subject's participation in the research, whether or not it is considered related to the subject's participation in the research.

Intercurrent illnesses or injuries should be regarded as adverse events. Abnormal results of diagnostic procedures are considered to be adverse events if the abnormality:

- results in study withdrawal
- is associated with a serious adverse event
- is associated with clinical signs or symptoms
- leads to additional treatment or to further diagnostic tests

Version: 2.4 10-29-2020

is considered by the investigator to be of clinical significance

Serious Adverse Event (SAE)

Adverse events are classified as serious or non-serious. A serious adverse event is any AE that:

- results in death;
- is life-threatening (places the subject at immediate risk of death from the event as it occurred);
- results in inpatient hospitalization or prolongation of existing hospitalization;
- results in a persistent or significant disability/incapacity;
- results in a congenital anomaly/birth defect; or
- based upon appropriate medical judgment, may jeopardize the subject's health and may require
 medical or surgical intervention to prevent one of the other outcomes listed in this definition
 (examples of such events include allergic bronchospasm requiring intensive treatment in the
 emergency room or at home, blood dyscrasias or convulsions that do not result in inpatient
 hospitalization, or the development of drug dependency or drug abuse).

Adverse Event Reporting Period

The study period during which adverse events must be reported is normally defined as the period from the initiation of any study procedures to the end of the study treatment follow-up. For this study, the study treatment follow-up is defined as 30 days following the last administration of study treatment.

Pre-existing Condition

A preexisting condition is one that is present at the start of the study. A pre-existing condition should be recorded as an adverse event if the frequency, intensity, or the character of the condition worsens during the study period.

General Physical Examination Findings

At screening, any clinically significant abnormality should be recorded as a preexisting condition. At the end of the study, any new clinically significant findings/abnormalities that meet the definition of an adverse event must also be recorded and documented as an adverse event.

Abnormal Laboratory Values

A clinical laboratory abnormality should be documented as an adverse event if any one of the following conditions is met:

- The laboratory abnormality is not otherwise refuted by a repeat test to confirm the abnormality
- The abnormality suggests a disease and/or organ toxicity
- The abnormality is of a degree that requires active management; e.g. change of dose, discontinuation of the drug, more frequent follow-up assessments, further diagnostic investigation, etc.

Hospitalization, Prolonged Hospitalization or Surgery

Any adverse event that results in hospitalization or prolonged hospitalization should be documented and reported as a SAE unless specifically instructed otherwise in this protocol. Any condition responsible for surgery should be documented as an AE if the condition meets the criteria for and adverse event.

Neither the condition, hospitalization, prolonged hospitalization, nor surgery are reported as an AE in the following circumstances:

- Hospitalization or prolonged hospitalization for diagnostic or elective surgical procedures for a preexisting condition.
- Surgery should not be reported as an outcome of an adverse event if the purpose of the surgery was elective or diagnostic and the outcome was uneventful.
- Hospitalization or prolonged hospitalization required to allow efficacy measurement for the study.
- Hospitalization or prolonged hospitalization for therapy of the target disease of the study, unless

Version: 2.4 10-29-2020

judged by the clinical investigator as worsening or increase in frequency of hospital admissions.

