1.4. Dose Rationale and Risk/Benefits

In the DPP trial, weight loss was proportional to diabetes prevention. There are no serious risks to losing weight at a reasonable rate. Dapagliflozin 10mg daily is the maximum daily dose and has been shown to increase glucose urinary excretion more than 5mg daily. Dapagliflozin 10mg/day has been assessed in combination with exenatide treatment in prediabetic patients for one year and shows similar safety and tolerability to previous trials in diabetic patients (35). Dapagliflozin 10mg/day is also in use for the DAPA-HF study in a study population that includes prediabetics (36). Another SGLT2i, empagliflozin, has been assessed in prediabetics at a comparably high dose (25mg/day) for two weeks and did not show AE among treated subjects (37). The SAE's associated with dapagliflozin include acute kidney injury, fall from orthostasis, gangrene of the perineum, and diabetic ketoacidosis. These risks will be mitigated in this study by monitoring subject status with biweekly phone check-ins with patients as well as monthly in-person visits during drug refill visits.

2. Study Objective

The primary objective is to determine whether SGLT2 inhibitors improve biomarkers of aging in older obese adults with pre-diabetes.

The secondary objective is to determine whether changes in aging-related biomarkers resulting from SGLT2i therapy are linked to changes in glucose metabolism and healthspan.

3. Study Design

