8.2. Recording of Adverse Events

At each contact with the subject, the investigator or study staff will seek information about adverse events by specific questioning and, if appropriate, by examination. Information on all AEs will be recorded immediately in the source document, and also in the appropriate AE section of the case report form (CRF). AEs will be tracked using the HSC IRB AE tracking form or data management tool (See Section 9.3) to be reviewed by Site Investigator on a monthly and ad hoc basis, depending on severity and expected/unexpected nature of the event. All subjects will have study compliance calls every two weeks during which AEs can also be reported.

All AEs occurring during the study period will be recorded. The clinical course of each event will be followed until resolution, stabilization, or until it has been determined that the study treatment or participation is not the cause. SAEs that are still ongoing at the end of the study period will be followed up to determine the final outcome. Any SAE that occurs after the study period and is considered to be possibly related to the study treatment or study participation will be recorded and reported per Institutional policy and according to FDA requirements.

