8.3. Reporting of Serious Adverse Events and Unanticipated Problems

Each participant will be evaluated for any adverse events (AE). Any incidents, experiences, and outcomes either reported by the subject to the PI or designated research staff or medical staff caring for the subject, and which meet AE criteria will be documented. Any AE reported as serious (SAE) requires submitting a Prompt Report Form to the IRB and, if deemed appropriate by PI, SAE and or unanticipated risks to subjects or others (UPIRSO) may be reportable to the Pepper Center DSMB. A copy of the SAE or UPIRSO prompt report is submitted to the Pepper DSMB for review as well as the NIA Program Officer within 24 hours of notification to PI. All AE that are not serious or UPIRSO will be summarized annually and submitted to the IRB and R&D Committees.

SAE and or UPIRSO will be reported per IRB policy and procedure. Events that do not involve AE or SAE (non-AE UPIRSO), and which are a result of study participation are also promptly reported to the IRB per local policy. The report will include a description of the event, when and how it was reported, as well as any official chart records or documentation to corroborate the event or the reporting of the event. All AE will be graded as mild, moderate, or severe. Any action resulting in a temporary or permanent suspension of this study (e.g. local site IRB actions) will be reported to FDA per IRB stipulations. Additionally, the PI will report SAE to the drug sponsor Astra-Zeneca.

Serious adverse events (SAE) still ongoing at the end of the study period will be followed up to determine the final outcome and or referred to participants' primary care provider. Any SAE that occurs after the study period that is considered to be possibly related to the study treatment or study participation will be recorded and reported per Institutional policy and according to FDA requirements.

Investigator responsibilities - The PI is responsible for:

- Reviewing all incidents, experiences, and outcomes that may represent UPIRSO.
- Determining whether event represents a possible UPIRSO
- Promptly reporting to IRB per local policy
- Contacting institutions involved
- Implementing actions necessary to eliminate immediate hazard
- Submitting follow up reports to IRB
- Submitting amendments to IRB, if applicable or stipulated

Version: 2.4 10-29-2020

Report SAE and UPIRSO immediately by phone and or secure email to:

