8.6. Stopping Rules

In the unlikely event that a study-related death or SAE occurs, the decision to stop the trial, either temporarily or permanently, will be the responsibility of the Designated Safety Officer in collaboration with the Principal Investigator.

There are several reasons why the researchers may need to end the subject's participation in the study. Some reasons are:

- 1. The researcher believes that it is not in the subject's best interest to stay in the study
 - Adverse drug reaction that does not resolve by dosing titration or if reaction is severe
 - b. Subject becomes ineligible to participate due to concomitant use of an exclusionary medication
- 2. Subject's health condition changes and needs treatment that is not allowed while participating in the study
- 3. Subject does not follow instructions from the research team.
- 4. The study is stopped

The research team will discuss options for medical care with the subject when participation in the study ends.

9. Data Handling and Record Keeping

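### Section 7.2 restricts the study's data to completers without exempting harms, no harms analysis set is defined, and the rule conflicts with section 4.4.1

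*Combined protocol and SAP*

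**What the plan says.** - **Inclusion rule.** Section 7.2: "The data included in this study will be only of completers". This is the only statement in section 7 about whose data are used. The change summary for version 2.1 describes the rule just as broadly, with no exemption for safety data.
- **Setting of the rule.** The same section opens with "Experimental results will be expressed as means ± SE" and goes on to ANCOVA, correlation and regression of biomarker, metabolic and healthspan outcomes. It does not mention AEs.
- **Withdrawn subjects.** Section 4.4.1 says that data collected before full withdrawal of consent go into the analysis. Section 4.4.2 covers subjects withdrawn early and has the investigator consult the statistician about incomplete data.
- **Ending participation.** Section 8.6 lists, among reasons why researchers may end participation, "Adverse drug reaction that does not resolve by dosing titration or if reaction is severe".
- **Recording of harms.** Section 8.2: "All AEs occurring during the study period will be recorded". The AE reporting period in section 8.1 runs to the end of follow-up, where "the study treatment follow-up is defined as 30 days following the last administration of study treatment".
- **Reporting of harms.** Section 8.3: "Any AE reported as serious (SAE) requires submitting a Prompt Report Form to the IRB", and "All AE that are not serious or UPIRSO will be summarized annually and submitted to the IRB and R&D Committees". Section 10.1 adds review by the data and safety monitoring board (DSMB) at least once a year.
- **Known risks.** Section 1.4: "The SAE's associated with dapagliflozin include acute kidney injury, fall from orthostasis, gangrene of the perineum, and diabetic ketoacidosis".

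**The concern.** A completer restriction affects harms differently from biomarkers. A biomarker change cannot be computed without the second sample, so restricting to completers partly reflects which data exist. An AE record exists whether or not the subject finishes. Under 8.6 the AE can also be the reason why the subject did not finish, so membership of the completer set depends on the outcome being counted. For drug reactions this can happen only in the dapagliflozin arm.

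Sections 7.1 and 7.2 say that this pilot will inform the size and design of a later trial. Tolerability in people aged 60 and over with prediabetes is part of what that trial would need. A tolerability table limited to completers would lean toward safety, and would lean further the more subjects the drug drove out. Nothing in the plan tells the analyst not to build the table that way.

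**Working it through.** The plan gives no power, effect size, standard deviation or AE rate by arm, so it has no figure to reproduce. The check is a reading of the text followed by an illustration.

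**Step 1: who is covered by which rule.** The plan does not define a completer. I take it to mean a subject whose participation was not ended before the post-intervention visits.

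| Subject | 7.2 read literally | 4.4.1 | Section 8 |
|---|---|---|---|
| Completes | Included | Not addressed | AEs recorded and reported to oversight |
| Withdraws own consent | Excluded | Included up to withdrawal | Same |
| Participation ended by researchers for a reaction (8.6) | Excluded | Not addressed | Same |

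The second row is a direct conflict between 7.2 and 4.4.1. In the third row the only rule on analysis inclusion is 7.2. Section 4.4.2 reaches these subjects but leaves their data to consultation. No row has a rule for the denominator or the arm-level count of reported harms.

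**Step 2: number randomised (assumption).** The inputs are 20 completers, 10 per arm (3.1), and 20% attrition (4.3). Section 4.3 does not say whether attrition comes before or after randomisation.
- If all of it comes after: N = 20 / (1 − 0.20) = 25, or 12 to 13 per arm, so 2 to 3 non-completers per arm.
- If all of it comes before: 20 are randomised and all complete, and the rule removes nobody.

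**Step 3: discontinuation for a reaction (assumed counts).** Let x of n subjects on dapagliflozin stop for a reaction while 10 complete. The rate among all who started is x/n. Among completers it is 0/10 for every x, because a subject whose participation ended is not a completer. Intervals are exact (Clopper-Pearson) 95%.

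| x / n | All who started | Completers only |
|---|---|---|
| 1/12 | 8.3% (0.2% to 38.5%) | 0/10 = 0% (0% to 30.8%) |
| 2/12 | 16.7% (2.1% to 48.4%) | same |
| 1/13 | 7.7% (0.2% to 36.0%) | same |
| 2/13 | 15.4% (1.9% to 45.4%) | same |
| 3/13 | 23.1% (5.0% to 53.8%) | same |

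**Step 4: any AE.** The effect is not confined to discontinuations. If 1 completer has an AE and 2 others stop for one, completers give 1/10 = 10%, while all who started give (1 + 2)/13 = 23.1%.

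**The case against.** The strongest reply is that 7.2 was never about harms. It sits among methods for continuous outcomes, and the sentence after it contrasts completers with a future intention-to-treat analysis, which is the language of an efficacy comparison. The protocol has no safety objective or endpoint, so there is no planned harm rate for the rule to restrict. Section 8 handles harms with no completer limit. All AEs are recorded and followed, serious ones go promptly to the IRB, the rest are summarised yearly, the DSMB reviews the study, and the safety officer in 8.5.1 compares events with assignment.

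Much of this stands. A reader might infer from 7.2 and 8.6 together that the trial will drop from its harm results the subjects whom the drug harmed. The documents do not support that. They leave open which subjects the harm results will use, and section 8 ensures that the events are captured and seen by oversight bodies.

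The reply does not close the gap. Oversight reports have no stated denominator, and the safety officer's comparison judges whether a serious event is related to the intervention; it does not produce rates by arm. Section 4.4.1 helps only where the subject withdraws consent, and there it contradicts 7.2.

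The size is also open to challenge. The illustrated counts let most or all drug-arm dropouts be drug reactions. Section 3.4 puts its rare and serious events below 1%; read as a combined rate, that is fewer than 13 × 0.01 = 0.13 expected among 13 subjects. It is an event frequency, though, and the documents give no rate of stopping for AEs. Section 8.6 is also permissive: researchers may end participation, not must. The intervals in the table overlap heavily, so the point is the direction of the bias and the forced zero, not a measured difference.

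**Conclusion.** The point holds as a defect of scope. Section 7.2 states an inclusion rule broader than its context needs, no harms set is defined, and the rule contradicts 4.4.1. If it is applied to reported harms as written, AE-related discontinuation among completers is zero whatever the true rate. That zero depends only on a subject whose participation ended not being a completer.

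The illustrated gap, 8% to 23% reported as 0/10, rests on two further assumptions: that the 20% attrition follows randomisation, and that 1 to 3 of 13 stop for a reaction. With no attrition after randomisation the gap is nil. The text should be corrected, but this does not show that harms will be hidden, and it does not bear on the conduct of safety oversight.

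**What to change.** 1. In 7.2, limit the completer sentence to the biomarker, metabolic and healthspan analyses.
2. Reconcile 7.2 with 4.4.1, so that one rule governs data collected before withdrawal, and say how subjects whose participation is ended by the researchers are treated.
3. Add a harms paragraph to section 7, for example: *Harms will be reported by assigned arm in all randomised subjects who started their assigned intervention, using every AE recorded under 8.2 through the end of the AE reporting period, whether or not the subject completed. For each arm we will give the number and percent of subjects with any AE, any SAE, and any AE leading to end of participation, with exact 95% confidence intervals.*
4. Because 8.1 closes the reporting period by reference to the last administration of study treatment, state what date that means in the counselling arm.

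The cost is a wording amendment and one small table built from data that 8.2 already requires. AE rates may look slightly less favourable than in a completer table. No change to dosing, visits or stopping rules is proposed.
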